6.2.3 Methods for assigning treatment groups

Not applicable. This is a single arm study.

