9.5.2.3 Patient reported outcomes

Summary measures of visit and overall compliance and completion rates will be derived for each PRO questionnaire. Refer to the SAP for details.

For PRO symptoms and health related quality of life endpoints, the main concepts of interest have been identified using a literature review, and detailed qualitative interviews SCLC patient and clinicians. The key symptoms were: cough, hemoptysis, dyspnea, chest pain, insomnia, fatigue and appetite loss.

Therefore we would like to pre-specify that an effective treatment would reduce time to deterioration and effect mean change from baseline in these key SCLC symptoms. The prespecified symptomatic endpoints are as follows: time to deterioration from baseline of cough, hemoptysis, dyspnea and chest pain from EORTC QLQ- LC13; and insomnia, fatigue and appetite loss from EORTC QLQ -C30; as well as average mean change of the key symptoms.

In addition, physical functioning and overall health status domains of the EORTC QLQ-C30 are furthermore pre-specified endpoints of interest.

The detail how this data will be analysed and the effect we would like to see to determine a symptomatic treatment effect will further be detailed and pre-specified in the SAP.

(a) EORTC QLQ-C30

If possible, time to symptom deterioration will be summarized for each of the 3 symptom scales (fatigue, pain, nausea/vomiting) and the 5 individual symptom items (dyspnea, insomnia, appetite loss, constipation, diarrhea). Similarly, a summary of QoL/function deterioration will be summarized for each of the function scales (physical, role, emotional, cognitive, and social) and global health status/QoL. This will be achieved by using Kaplan-Meier product limit methods to provide summaries of the number and percentage of patients experiencing a clinically meaningful deterioration or death, the median time to deterioration together with the corresponding 95% CIs, as well as the Kaplan-Meier plots.

Summaries of original and change from baseline values of each symptom scale/item, the global HRQoL score, and each functional domain will be reported by visit. Details will provided in the SAP.

Definition of clinically meaningful changes

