#### 4.1.3 Definition of comparison drug exposure

Not applicable.

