#### Endpoints analyzed:

- Change from baseline in European Organisation for Research and Treatment of Cancer Quality of Life Questionnaire Core 30 items (EORTC QLQ-C30) and Questionnaire-Lung Cancer 13 (EORTC QLQLC13):

Scores for the QLQ-C30 and QLQ-LC13 questionnaires will be calculated according to published scoring manuals or the developer's guidelines. Raw scores from scales in both questionnaires will be standardized by linear transformation so that they range from 0 to 100. Higher scores for symptom items indicate greater symptom severity, while higher scores for function and global health status/QoL items indicate better function and health status/QoL. For both questionnaires, a clinically meaningful change will be prespecified as an absolute change in score from baseline of  $\geq 10$  points (either deterioration or improvement). For the five key disease-related symptoms (cough, dyspnea, and chest pain [QLQ-LC13], and fatigue and appetite loss [QLQ-C30]), changes at each visit from baseline to disease progression or end of follow-up (whichever came first) will be analyzed using a mixed model for repeated measures (MMRM) to derive an overall adjusted mean change from baseline, reflecting the average treatment effect over visits. The model assumes PROs will be collected at multiple visits per

patient. Visits with >75% missing data will be excluded from the analysis. The MMRM included treatment, age at baseline (<65 vs ≥65 years), sex, smoking history (smoker vs non-smoker) and visit interaction as fixed factors, and baseline score as a covariate; the model further adjusted for baseline score-by-visit interaction.

Summaries of original and change from baseline values of each symptom scale/item, the global HRQoL score, and each functional domain will be reported by visit.

Time to symptom deterioration and time to quality of life / function deterioration (defined in 4.2.2) will be analyzed by product limit methods to provide summaries of the number and percentage of patients experiencing a clinically meaningful deterioration or death, the median time to deterioration together with the corresponding 95% CIs, as well as the Kaplan-Meier plot. An stratified log-rank test adjusted for therapy will be used with HR s and 95% CIs calculated using a stratified Cox proportional hazards model.

Symptom improvement rate and Quality of life / function improvement (defined in 4.2.2) will be summarized.

- Changes from baseline in PRO-CTCAE:

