## 6. BIAS

### 6.1 Methods to minimize bias

#### 6.1.1 Patient enrolment

This is a single arm, open label study; no randomization or blinding will be performed.

Investigators should keep a record (ie, the patient screening log) of patients who entered screening.

At screening/baseline (Days -28 to -1), the Investigators or suitably trained delegate will:

- Obtain signed informed consent before any study specific procedures are performed. If laboratory or imaging procedures were performed for alternate reasons prior to signing consent, these can be used for screening purposes with consent of the patient. However, all screening laboratory and imaging results must have been obtained within 28 days of inclusion.
- Obtain a unique enrolment number (E-code), through the Interactive Web Response System (IWRS). This number is the patient's unique identifier and is used to identify the patient on the electronic case report forms (eCRFs).
- Determine patient eligibility based on inclusion/exclusion criteria. If the patient is ineligible and not included, the IWRS should be contacted to terminate the patient in the system.

Patients will start treatment on Day 1. Treatment should start no more than 3 working days after being included. Patients must not be included and treated unless all eligibility criteria have been met.

If a patient withdraws from participation in the study, then his or her enrolment code cannot be reused.

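### SAP 5.2.2 plans a treatment term, a log-rank test and hazard ratios for the PRO endpoints of a single-arm study without naming any groups to compare

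*SAP*

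**What the plan says.** Both documents are clear that there is one arm. SAP 6.1.1 states: "This is a single arm, open label study; no randomization or blinding will be performed". Protocol 6.2.3, on assigning treatment groups, reads: "Not applicable. This is a single arm study". SAP 4.1.3, headed "Definition of comparison drug exposure", is marked as not applicable. Protocol 9.1 has no formal hypothesis, and the synopsis (Protocol 1.2) describes every analysis as descriptive.

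SAP 5.2.2 then specifies three things for the EORTC questionnaires that presuppose a comparison:

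- **Model term.** For change from baseline in five key symptoms, "The MMRM included treatment, age at baseline", together with sex, smoking history, an interaction with visit whose partner is not named, baseline score and baseline-by-visit.
- **Label.** The overall adjusted mean change from baseline is described as "reflecting the average treatment effect over visits".
- **Test and hazard ratio.** For time to deterioration, "An stratified log-rank test adjusted for therapy will be used with HR s and 95% CIs" from a stratified Cox model. Neither the compared groups nor the strata are named.

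The protocol plans less for the same endpoint. On time to deterioration, Protocol 9.5.2.3 says: "This will be achieved by using Kaplan-Meier product limit methods to provide summaries" of counts, medians with 95% CIs, and plots. The table of pre-planned analyses in Protocol 9.5.2.2 also lists Kaplan-Meier estimates only.

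**The concern.** A treatment effect, a log-rank test and a hazard ratio each need at least two groups. Here every patient is on the same regimen, and the SAP names no other grouping for these endpoints.

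Two things are at stake. First, the log-rank and Cox sentence cannot be carried out until someone supplies groups and strata. As written, that choice would be made by analysts who can already see open-label data; SAP 7 schedules output from section 5.2.2 for February 2022, and SAP 6.3 has no multiplicity adjustment. Second, a within-patient change from baseline would be reported under a treatment-effect label. Such a change mixes any effect of the regimen with regression to the mean and with selective drop-out, and one arm cannot separate them.

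**Working it through.** The plan gives no figure on this point to reproduce, so the check is algebraic.

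**Inputs.** One arm (SAP 6.1.1, SAP 4.1.3, Protocol 6.2.3). About 85 patients (SAP 2.2). Model terms from SAP 5.2.2, plus a visit main effect. Assumption: V = 6 post-baseline visits, for illustration only; the result does not depend on V.

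**Mixed model.** Without treatment, the fixed-effect columns are the intercept (1), age, sex and smoking (3), baseline score (1), visit (V − 1) and baseline-by-visit (V − 1). That is 2V + 3, or 15 when V = 6. In one arm the treatment column is constant, so it equals the intercept; a treatment-by-visit column equals the matching visit column.

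| Fixed effects | Columns | Rank |
|---|---|---|
| No treatment term | 15 | 15 |
| Plus treatment | 16 | 15 |
| Plus treatment and treatment-by-visit | 21 | 15 |
| Platinum type used as treatment, with its visit interaction | 21 | 21 |

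The rank stays at 15 when study treatment is added, so the treatment terms contribute 0 estimable degrees of freedom. The other 15 columns are intact, so the adjusted mean change from baseline is still estimable.

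**Log-rank test.** At event time j, with d_j events among n_j at risk, of whom n_1j are in group 1:

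- E_j = d_j × n_1j / n_j
- V_j is proportional to d_j × (n_1j / n_j) × (1 − n_1j / n_j)

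With one group n_1j = n_j. Then E_j = d_j, so observed minus expected is 0, and V_j = 0. The statistic is 0/0 on 1 − 1 = 0 degrees of freedom. Stratifying does not help, because every stratum also contributes 0 and 0.

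**Cox model.** A covariate with the same value z for everyone puts exp(βz) in both the numerator and the denominator of each partial-likelihood term. It cancels, the likelihood is flat in β, and no hazard ratio can be estimated.

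**If therapy means platinum type.** This is an assumption; SAP 5.2.2 does not say it.

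- As the stratum only, the log-rank test still has no groups within strata and the result above stands.
- As the compared factor, the contrast is estimable (rank 21 of 21) provided both platinum agents are used. But the investigator chooses the platinum agent (Protocol 6.1.2.2) and patients may switch (Protocol 8.4.5.2); SAP 5.2.2 does not say how switchers are classified. The result would be a non-randomised subgroup contrast within patients who all receive durvalumab.

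**The case against.** The strongest defence is that therapy means platinum type. SAP 5.2.1 uses platinum received as a subgroup factor, with Cox hazard ratios and log-rank tests, and two levels can occur. This stands to the extent that the PRO hazard ratios are not undefined on every possible reading. It does not rescue the text. Where SAP 5.2.1 wants that contrast it names cisplatin and carboplatin; SAP 5.2.2 does not.

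A reader might also infer that the PRO analyses as a whole cannot be run. The documents do not support that. The stated target of the model is an adjusted mean change from baseline, which survives the loss of a redundant term. The Kaplan-Meier counts, medians, intervals and plots in the same section are usable as written, as are the by-visit summaries and improvement rates.

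Nor does the point extend to every hazard ratio in the plan. Those for PFS, DoR and OS in SAP 5.2.1 compare named subgroups.

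Finally, regression to the mean and drop-out affect any within-arm change, including the one recommended below. Relabelling prevents a wrong claim; it does not remove those biases. The consequences are also bounded: these are secondary, descriptive endpoints, and no decision rule rests on a PRO p-value.

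**Conclusion.** The concern holds in a limited form. SAP 5.2.2 contains a model term, a label, and a test with hazard ratios that do not fit a single-arm study, and it names no groups or strata that would give them meaning. If study treatment is meant, the treatment term and the log-rank test have 0 degrees of freedom and the hazard ratio is undefined, for any sample size and any number of visits. If platinum type is meant, the SAP must say so: as a stratum it leaves nothing to compare, and as the compared factor it does not estimate an effect of durvalumab plus platinum-etoposide. The text needs correcting on either reading. The primary safety endpoints are untouched.

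**What to change.** Amend SAP 5.2.2 as follows.

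1. Remove treatment from the mixed model and drop the treatment-effect label. List the fixed effects as visit (categorical), baseline score, baseline-by-visit, age, sex and smoking.
2. Define the estimate as the within-arm adjusted mean change from baseline, averaged over visits, with 95% CI, and state that it is not to be interpreted as a causal treatment effect. Protocol 9.5.2.3 also speaks of a symptomatic treatment effect and leaves the detail to the SAP, so this sentence settles how that phrase is to be read.
3. For time to deterioration, do one of two things. Either delete the log-rank and Cox sentence and keep the Kaplan-Meier summaries, which restores agreement with Protocol 9.5.2.2 and 9.5.2.3. Or, if a platinum contrast was intended, name the compared groups and the strata, say how patients who switch are classified, and label it an exploratory non-randomised subgroup comparison.

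The cost is SAP wording only: no new data and no change to study conduct. It should be settled before any output from section 5.2.2 is produced.

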3. OBJECTIVES AND ENDPOINTS

Table 3 Study objectives

Primary Objective:	Endpoint/Variable:
To describe safety profile of durvalumab in combination with platinum–etoposide as first-line treatment for patients with ES-SCLC and also as monotherapy maintenance treatment.	Incidence of grade ≥ 3 AEs Incidence of imAE

Secondary Objective:	Endpoint/Variable:
To describe effectiveness of durvalumab in combination with platinum–etoposide as first-line treatment for patients with ES-SCLC.	Progression Free Survival (PFS). PFS rate at 6 months and at 1 year (PFS6, PFS12). Objective Response Rate (ORR): using site investigator assessments according to RECIST 1.1. Duration of Response (DoR) DoR at 1 year (DoR12). Time to Treatment Discontinuation (TTD). Overall Survival (OS). The OS rate at 6, 12 and 18 months. Time to event endpoints measured as time from first Durvalumab dose.
To describe the impact of durvalumab in combination with platinum–etoposide as first-line treatment for patients with ES-SCLC on patients’ disease-related symptoms and Health Related Quality of Life (HRQoL) and (PROs).	Changes in vital signs, physical findings, and clinical laboratory results during and following study treatment administration Change from baseline in European Organisation for Research and Treatment of Cancer Quality of Life Questionnaire Core 30 items (EORTC QLQ-C30). Change from baseline in European Organisation for Research and Treatment of Cancer Quality of Life Questionnaire-Lung Cancer 13 (EORTC QLQ-LC13).
To describe health care resources use related to management of ES-SCLC patients treated with durvalumab in combination with platinum–etoposide as first-line treatment.	Changes from baseline in PRO-CTCAE. 
- Number and length of hospitalizations- Number of visits to oncology service- Number of emergency visits- Number of outpatient visits- Number of imaging tests- Number of biopsy-related procedures- Treatment dose, duration, number of cycles

Secondary Objective:	Endpoint/Variable:

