8.2.7.3 PRO-CTCAE

The PRO-CTCAE is included to address tolerability from the patients’ perspective. It was developed by the National Cancer Institute (NCI). The PRO-CTCAE will only be administered in those countries where a linguistically validated version exists. It was developed in recognition that collecting symptom data directly from patients using PRO tools can improve the accuracy and efficiency of symptomatic AE data collection. This was based on findings from multiple studies demonstrating that physicians and nurses underestimate symptom onset, frequency, and severity in comparison with patient ratings (Antonia et al 2014, Litwin et al 1998, Sprangers and Aaronson 1992). These symptoms have been converted to patient terms (eg, the CTCAE term “myalgia” has been converted to “aching muscles”). For several symptoms, like fatigue and pain, additional questions are asked about symptom frequency, severity, and interference with usual activities. The items included in the PRO-CTCAE have undergone extensive qualitative review among experts and patients. These items have been extensively evaluated by cancer patients to be clear, comprehensible, and measure the symptom of interest. In this study, only items that are considered relevant for the study, site of cancer, and cancer treatment are selected.

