PFS (days) = Date of event or Censor date – treatment start date +1

Patients who have not progressed or died at the time of analysis will be censored at the time of the latest date of assessment from their last evaluable assessment. However, if the patient progresses or dies after 2 or more missed visits, the patient will be censored at the time of the latest evaluable assessment prior to the 2 missed visits. If the patient has no evaluable visits or does not have baseline data, he/she will be censored at Day 1 unless he/she dies within 2 visits of baseline, in which case the date of death is the event date.

OS: Defined as the time from the first date of treatment until death due to any cause.

OS (days) = Death date or Censor date - treatment start date +1

Any patient not known to have died at the time of analysis will be censored based on the last recorded date on which the patient was known to be alive.

ORR: Based on Investigator–assessed response to treatment of CR and PR, per RECIST1.1.

DoR: Defined as the time from the date of first documented response per RECIST1.1 until the first date of documented progression per RECIST1.1 or death in the absence of disease progression.

DoR (days) = Date of PFS event or censoring – Date of first response +1

The end of response should coincide with the date of progression or death from any cause used for the PFS endpoint. If a patient does not progress following a response, then the patients' DoR will be censored at the PFS censoring time. DoR will not be defined for those patients who do not have a documented response.

Time to symptom deterioration (EORTC QLC-C30 and QLC-LC13): Defined as the time from start of study drug until the date of the first clinically meaningful symptom deterioration that is confirmed at the subsequent assessment or death (by any cause) in the absence of a clinically meaningful symptom deterioration, regardless of whether the patient withdraws from study drug or receives another anticancer therapy prior to symptom deterioration.

Change from baseline (EORTC QLC-C30 and QLC-LC13, PRO-CTCAE): Defined as the post-treatment value minus the value at baseline. The % change from baseline will be calculated as (postbaseline value - baseline value) / baseline value x 100.

Treatment duration: Defined as Treatment end date - Treatment start date +1; will be summarized.

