Patients whose QoL (as measured by EORTC QLQ-C30) have not shown a clinically meaningful deterioration and who are alive at the time of the analysis will be censored at the time of their last PRO assessment where the QoL/function could be evaluated. Also, if QoL deteriorates after 2 or more missed PRO assessment visits or the patient dies after 2 or more missed PRO assessment visits, the patient will be censored at the time of the last PRO assessment where QoL/function could be evaluated. If a patient has no evaluable visits or does not have baseline data, he/she will be censored at Day 1.

Symptom improvement rate

The symptom improvement rate will be defined as the number (%) of patients with 2 consecutive assessments at least 14 days apart that show a clinically meaningful improvement (a decrease from baseline score ≥ 10 points for EORTC QLQ-C30 symptom scales/items) in that symptom from baseline.

Quality of life/function improvement rate

The QoL/function improvement rate will be defined as the number (%) of patients with 2 consecutive assessments at least 14 days apart that show a clinically meaningful improvement (an increase from baseline score ≥ 10 points for EORTC QLQ-C30 functional scales and global health status/QoL) in that scale from baseline.

(b) EORTC QLQ-LC13

Data will be summarized for each of the symptom items in EORTC QLQ-LC13 as outlined above for EORTC QLQ-C30.

Summaries of original and change from baseline values of each symptom (dyspnea, cough, hemoptysis, chest pain, arm/shoulder pain, and other pain) and each treatment-related side effect (sore mouth, dysphagia, peripheral neuropathy, and alopecia) will be reported by visit. Details will be provided in the SAP.

(c) **PRO-CTCAE**

PRO-CTCAE data will be presented using summaries and descriptive statistics. Further details will be provided in the SAP.

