##### Endpoints analyzed:

- Change from baseline in European Organisation for Research and Treatment of Cancer Quality of Life Questionnaire Core 30 items (EORTC QLQ-C30):

This analysis will be performed for the Intention-to-Treat population (ITT). For the following endpoints, change from baseline is defined as the post-treatment value minus the value at baseline. The % change from baseline will be calculated as:

$$(\text{Postbaseline value} - \text{baseline value}) / \text{baseline value} \times 100.$$

The **EORTC QLQ-C30 v3 questionnaire** is included for the purpose of assessing HRQoL and is a well-established measure of HRQoL/health status. It assesses HRQoL/health status through 9 multi-item scales: 5 functional scales (physical, role, cognitive, emotional, and social), 3 symptom scales (fatigue, pain, and nausea and vomiting), and a global health and quality-of-life (QoL) scale. Six single-item symptom measures are also included dyspnea, insomnia, appetite loss, constipation, diarrhea, and financial difficulties. For each of the 15 domains, final scores are transformed such that they range from 0 to 100, where higher scores indicate greater functioning, greater HRQoL, or greater level of symptoms .

The principle for scoring these scales is the same in all cases:

- Estimate the average of the items that contribute to the scale; this is the raw score.
- Use a linear transformation to standardise the raw score, so that scores range from 0 to 100; a higher score represents a higher ("better") level of functioning, or a higher ("worse") level of symptoms.

For all scales, the *RawScore*, *RS*, is the mean of the component items:

$$\text{RawScore} = \text{RS} = (I_1 + I_2 + \dots + I_n)/n$$

Then for **Functional scales**:

$$\text{Score} = \left\{ 1 - \frac{(\text{RS} - 1)}{\text{range}} \right\} \times 100$$

For **Symptom scales/ items** and **Global health status/ QoL**:

$$\text{Score} = \left\{ \frac{(\text{RS} - 1)}{\text{range}} \right\} \times 100$$

The following outcomes will be analysed for this endpoint:

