- Quality of life/function improvement rate: defined as the number (%) of patients with 2 consecutive assessments at least 14 days apart that show a clinically meaningful improvement (an increase from baseline score  $\geq 10$  points for EORTC QLQ-C30 functional scales and global health status/QoL) in that scale from baseline.
- Change from baseline in European Organisation for Research and Treatment of Cancer Quality of Life. Questionnaire-Lung Cancer 13 (EORTC QLQLC13):

This analysis will be performed for the Intention-to-Treat population (ITT). For patients with SCLC, a disease-specific 13-item self-administered questionnaire for lung cancer was developed to be used in conjunction with the EORTC QLQ-C30. It comprises both multi-item and single-item measures of lung cancer-associated symptoms (i.e., coughing, haemoptysis, dyspnoea, and pain) and side effects from conventional

chemotherapy and radiotherapy (i.e., hair loss, neuropathy, sore mouth, and dysphagia). Similar to the EORTC QLQ-C30, all questions except one have a 4-point scale: (not at all, a little, quite a bit and very much). One question (no. 43, —Did you take any medicine for pain?) has a response option (Yes; No). The scoring approach for the EORTC QLQ-LC13 is similar to the EORTC QLQ-C30.

The following outcomes will be analysed for this endpoint:

- Time to symptom deterioration
- Symptom improvement rate

- Changes from baseline in PRO-CTCAE:

The **PRO-CTCAE** is included to address tolerability from the patients' perspective. It was developed in recognition that collecting symptom data directly from patients using PRO tools can improve the accuracy and efficiency of symptomatic AE data collection.

In this study, only items that are considered relevant for the study, site of cancer, and cancer treatment are selected.

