PRO-CTCAE data will be presented using summaries and descriptive statistics for categorical data for each question of the questionnaire.

### 5.2.3 Secondary outcome 3

- To describe health care resources use related to management of ES-SCLC patients treated with durvalumab in combination with platinum- etoposide as first-line treatment. It will be described the overall costs and health care resources use as well as costs and health care resources use adjusted by time in years.

The following data will be described as appropriate:

- Number of hospitalizations (Categorical and continuous)
- Length of hospitalizations: time from date of admission to discharge date (Continuous).
- Number of visits to oncology service (Categorical and continuous)
- Number of emergency visits (Categorical and continuous)
- Number of outpatients visits (Categorical and continuous)
- Number of imaging tests (Categorical and continuous)
- Number of biopsy-related procedures (Categorical and continuous)
- Listing of treatments administered, including: Treatment name, dose, duration and number of cycles
- Assessment of health economic resource: Costs associated with HCRU use will be quantified by multiplying the natural units of use of each resource by the cost of each resource retrieved from Spanish databases

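### SAP 5.2.2 names change from baseline in PRO-CTCAE as an endpoint but specifies only per-question categorical summaries, which do not yield a within-patient change

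*SAP*

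**What the plan says.** - **Endpoint.** Protocol Table 3 lists "Changes from baseline in PRO-CTCAE" among the secondary endpoints. SAP 4.2.2.2 and SAP 5.2.2 carry the same endpoint as a bullet heading.
- **Definition.** Protocol 9.4 names the instrument: "Change from baseline (EORTC QLC-C30 and QLC-LC13, PRO-CTCAE): Defined as the post-treatment value minus the value at baseline".
- **Purpose.** Protocol 8.2.7.3: "The PRO-CTCAE is included to address tolerability from the" patients' perspective. SAP 4.2.2.2 says the same.
- **Method in the protocol.** Section 9.5.2.3(c): "PRO-CTCAE data will be presented using summaries and descriptive statistics. Further details will be provided in the SAP".
- **Method in the SAP.** Section 5.2.2: "PRO-CTCAE data will be presented using summaries and descriptive statistics for categorical data for each question of the questionnaire". Nothing else stands under that bullet. The opening of SAP section 5 says that categorical variables are summarised by counts and percentages.
- **Comparators within the plan.** For the EORTC questionnaires, SAP 5.2.2 asks for "Summaries of original and change from baseline values of each symptom scale/item", by visit. For adverse events, SAP 4.2.1 applies a treatment-emergent rule that refers back to baseline.

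**The concern.** The protocol defers the PRO-CTCAE method to the SAP, so the SAP is the last place where the endpoint can be turned into a table. The sentence there describes a different quantity from the one in the bullet heading: a distribution of responses, not a change within a patient.

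This matters because the symptoms overlap. Protocol 2.1 describes these patients as symptomatic. Protocol 9.5.2.3 lists cough, dyspnea, fatigue and appetite loss among the key disease symptoms. Protocol 2.3.2.1 lists fatigue, cough, decreased appetite, dyspnea and nausea as the adverse events seen in at least 20% of patients on durvalumab monotherapy. Four of those five are also key disease symptoms. With one arm and no control (protocol 6.2.1), each patient's own baseline is the only internal reference. A table without that reference leaves the reader unable to tell a symptom that was already there from one that worsened after treatment began.

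**Working it through.** The documents state no figure for PRO-CTCAE, so there is none to reproduce. The check is a comparison of texts, followed by arithmetic on assumed rates to show what the gap could do.

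**Step 1: does the stated method deliver the endpoint?**

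| Data | Quantity named | Baseline reference in the analysis text |
|---|---|---|
| EORTC QLQ-C30 and QLQ-LC13 | Change from baseline | Yes: original and change values by visit (SAP 5.2.2) |
| Adverse events | Treatment-emergent incidence | Yes: absent at baseline, or worse than at baseline (SAP 4.2.1) |
| PRO-CTCAE | Change from baseline | None stated: no change score, visit, baseline column, shift table or worst-score rule (SAP 5.2.2) |

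**Step 2: would by-visit frequencies including baseline be enough?** Suppose 40% of 85 patients report a symptom at baseline and 40% at a later cycle (assumed).
- 0.40 × 85 = 34 patients on each occasion, and 85 − 34 = 51 were symptom-free at baseline.
- If the same 34 patients report it twice, 0 are newly symptomatic.
- If all 34 resolve and 34 of the other 51 develop it, 34 are newly symptomatic.

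Both cases give identical frequencies. Only a cross-classification of each patient's baseline and later responses separates them.

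**Step 3: how far could a raw table lie from a baseline-referenced one?** Treat an item as present or absent. Let *b* be the share with the symptom at baseline, *p* the share of those who still report it on treatment, and *w* the share of symptom-free patients who develop it. All three are assumptions; only N = 85 is from the plan (protocol 9.2).
- Raw share reporting the symptom: R = b·p + (1 − b)·w
- Newly symptomatic share: S = (1 − b)·w

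| b | p | w | R | R × 85 | S | S × 85 |
|---|---|---|---|---|---|---|
| 20% | 50% | 0% | 0.10 + 0 = 10% | 8.5 | 0% | 0 |
| 60% | 100% | 0% | 0.60 + 0 = 60% | 51 | 0% | 0 |
| 20% | 50% | 10% | 0.10 + 0.08 = 18% | 15.3 | 8% | 6.8 |
| 60% | 100% | 10% | 0.60 + 0.04 = 64% | 54.4 | 4% | 3.4 |

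This illustration ignores a symptom that was present and became more severe. A shift table on the graded responses would capture that.

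**Step 4: are the data there?** Protocol 8.2.7 has the questionnaires completed on day 1 of every cycle, and the note under Table 1 places assessments on treatment days before infusion. A pre-dose value should therefore exist.

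**The case against.** The strongest reply is that the SAP is silent, not wrong. The sentence sits under a heading that still names change from baseline. SAP 4.2.2.2 also says "For the following endpoints, change from baseline is defined as the post-treatment value minus the value at baseline", and PRO-CTCAE comes later in the same list. A programmer could lay out each question by visit with a baseline column and remain within the text. This stands in part: the SAP does not exclude a baseline column. But the definition is placed under the QLQ-C30 bullet, nothing requires the column, and step 2 shows that the column alone would not give a within-patient change.

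A reader might infer that the plan reports pre-existing symptoms as treatment toxicity. The documents do not support that. The primary endpoints, grade ≥3 adverse events and immune-mediated events, are taken from the adverse event eCRF under a treatment-emergent rule (SAP 4.2.1), and PRO-CTCAE does not feed them. Misattribution is a risk for someone reading the PRO-CTCAE tables; it is not something the plan does.

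A reader might also take PRO-CTCAE to be the only patient-reported view of side effects. It is the only instrument included for the stated purpose of tolerability. However, QLQ-LC13 covers hair loss, neuropathy, sore mouth and dysphagia, and QLQ-C30 covers nausea and vomiting, constipation, diarrhea and fatigue. Change from baseline is planned for both, which limits what is lost.

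Finally, a worst-score summary is not literally the difference defined in protocol 9.4, and it cannot isolate toxicity. Both points are fair and are dealt with under the fix.

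**Conclusion.** The point holds as a mismatch between a named endpoint and its analysis. As written, SAP 5.2.2 does not produce change from baseline in PRO-CTCAE, so symptoms present before treatment may not be separable from worsening on treatment when the tables are read. The finding rests on the texts alone.

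Its size is unknown. The documents give no baseline PRO-CTCAE rates and do not list the selected items, so the overlap with disease symptoms is plausible but not shown item by item. The ranges above follow from the assumed rates and are not estimates for this trial.

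The consequence is moderate. This is a descriptive secondary endpoint in a study without formal hypotheses, and the primary safety results do not depend on it. It is still worth correcting: the endpoint is named in both documents, and the data needed should already be collected.

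**What to change.** In SAP 5.2.2, replace the PRO-CTCAE sentence with a specification for each item:

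1. The distribution of responses by cycle, including baseline. Baseline is the last assessment before the first IP dose, as in protocol 9.5.
2. A shift table of baseline response against worst post-baseline response.
3. The number and percentage of patients whose worst post-baseline score exceeds their baseline score, with an exact 95% CI. The denominator is patients with a baseline and at least one post-baseline response.

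A split by chemotherapy and monotherapy phase is optional. The SAP should say that item 3 compares post-treatment with baseline at the worst visit. If a literal match to protocol 9.4 is wanted, the difference by cycle can be added from the same data.

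**Cost.** SAP wording and a short set of tables per item; no new data collection. SAP section 7 already schedules output from 5.2.2 for February 2022, and the same specification should govern that output. For precision, 17 of 85 patients worsening (20%) would have an exact interval of 12.1% to 30.1%, as in the protocol 9.2 precision table; missing forms would widen it.

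**Limits to state in the SAP.** Patients without a baseline form drop out of items 2 and 3. The worst score tends to rise with the number of visits. In a single arm, worsening may reflect disease progression, so the result should be labelled worsening from baseline and not treatment toxicity.
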